9.4 Overdose

The study drugs are planned to be administered by trained study staff. Administration will be performed in accordance with the IB and instructions in a study-specific manual. Any incidence of overdose should be recorded as an SAE.

No clinical data are available regarding overdose with WVE-003. As with any agent, if overdose occurs, general supportive measures and close observation should be instituted. Misuse of the study drug for illegal purposes is not expected in this study as patients have no direct access to the study drugs.

10 PREGNANCIES

If a patient becomes pregnant during the course of the study, the pregnancy must be reported, and monitoring of the patient and child should be conducted until the pregnancy outcome.

If a female patient becomes pregnant during the study, she must be discontinued from the study drug although the patient may continue to be followed in the study. The Medical Monitor should be notified by the Investigator, and a Pregnancy Notification Form should be completed. The patient should be followed until the outcome of the pregnancy is known.

Pregnancy in and of itself is not an SAE. However, complications of the pregnancy should be reported to the Sponsor within 24 hours of knowledge by the Investigator (e.g., if the mother is hospitalized for dehydration), and an SAE form must be completed.

Based on the expected date of delivery, the Sponsor will attempt follow-up to determine the outcome of the pregnancy.

11 STATISTICAL METHODS

A separate statistical analysis will be performed for Period 1 (SAD) and Period 2 (MAD). Patients receiving placebo will be pooled to form a placebo control group for Period 1 and Period 2.

11.1 Sample Size Determination

The sample size was not calculated on the basis of statistical hypothesis testing; however, the number of patients is sufficient for a Phase 1b/2a assessment of safety, tolerability, PK, and early measures of PD and clinical effects.

11.2 Disposition of Patients

Screened patients are defined as any patient who signed informed consent. Randomized patients consist of all patients, with a signed informed consent, randomized via the IRT.

11.2.1 Analysis Populations

The following study populations will be evaluated:

- Safety population: randomized patients who receive at least 1 dose of study treatment.
- Pharmacokinetic population: the subset of the safety population with at least 1 postdose PK measurement
- Pharmacodynamic population: the subset of the safety population with at least 1 postdose PD measurement

- Clinical efficacy population: the subset of the safety population with at least 1 postdose measurement

11.3 Statistical Methods

Summary statistics (n, mean, standard deviation [SD], median, minimum and maximum values for continuous variables, and number [%] of patients in each category for categorical variables) will be provided by dose group and visit. Baseline for the Period 2 analysis of clinical effects and pharmacodynamic endpoints will be the measurement prior to the first dose of study drug in Period 2 for both new Period 2 patients and Period 1 rollover patients. Sensitivity analysis will include using the measurement prior to first dose in Period 1 for the Period 1 rollover patients.

11.3.1 Study Drug Exposure and Compliance

The extent of study drug exposure and compliance will be summarized by dose group for the safety population.

11.3.2 Analysis of Clinical Effects Endpoints

The change from baseline of the clinical effects endpoints will be analyzed using a mixed model for repeated measures (MMRM). The MMRM will include the relevant baseline measure and factor variables for time, dose group and time by dose group interaction. An unstructured variance-covariance matrix will be used to model the within-subject variability. If the MMRM with unstructured variance-covariance matrix does not converge, a compound symmetric structure will be used. Least square means of the time and dose group combinations and contrasts to placebo will be provided with 95% confidence intervals and p-values.

11.3.3 Analysis of Pharmacodynamic Endpoints

Pharmacodynamic biomarkers include (but are not limited to) mHTT, wtHTT, and NfL in the CSF and/or plasma. The NfL measurements will be log-transformed, and analysis will be based on the transformed data.

The MMRM described for the analysis of the clinical effects endpoints will be applied with the exception that the baseline measure will not be included.

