Statistical Methods: 
The sample size was not calculated on the basis of statistical hypothesis testing; however, the number of patients is sufficient for a Phase 1b/2a assessment of safety, tolerability, PK, and early measures of PD and clinical effects.
 
Summary statistics (n, mean, standard deviation [SD], median, minimum and maximum values for continuous variables, and number [%] of patients in each category for categorical variables) will be provided by dose group and visit.
 
The change from baseline for PD and clinical effects endpoints will be summarized using a mixed model for repeated measures (MMRM). The MMRM will be used to construct 95% confidence intervals and to test for differences between dose groups and placebo.
 
Treatment-emergent AEs (TEAEs) and treatment-emergent SAEs will be summarized for each dose group based on MedDRA coding of verbatim terms reported by investigators.
			

TABLE OF CONTENTS

Clinical Protocol Approval Form	2
Principal Investigator's Agreement	3
Protocol Synopsis	4
Table of Contents	11
List of Tables	14
List of Figures.....	14
List of Abbreviations	15
1 Introduction.....	18
1.1 Huntington's Disease	18
1.2 Investigational Product WVE-003.....	18
1.3 Nonclinical Data	19
1.4 Clinical Experience	21
2 Rationale for the Study	21
2.1 Rationale for the Doses and the Dosing Regimen	22
2.2 Anticipated Benefit/Risk	24
2.3 Current Status of the Study and Dosing Paradigms as Recommended by the DEC and SMC.....	24
3 Study Objectives	25
4 Study Design.....	25
4.1 Study Design Overview.....	25
4.1.1 Prescreening Phase	29
4.1.2 Screening Phase.....	29
4.1.3 Period 1 (Single-ascending-dose Period).....	30
4.1.4 Period 2 (Multiple-ascending-dose Period)	31
4.1.5 Early Termination Visit	32
4.2 Schedule of Assessments.....	32
4.3 Study Endpoints	48
4.4 Safety Considerations	49
4.4.1 Dose Escalation Committee Review	49
4.4.2 Safety Monitoring Committee Review	49
4.4.3 Stopping Criteria	50
4.4.4 Communication of Emergent Safety Concerns.....	52
4.4.5 Considerations Due to COVID-19 Pandemic	52
5 Patient Selection and Withdrawal Criteria	53
5.1 Inclusion Criteria	53
5.2 Exclusion Criteria	54
5.2.1 Additional Study Restrictions.....	56
5.3 Withdrawal and Discontinuation	57
5.3.1 Withdrawal of Patients From the Study.....	57
5.3.2 Discontinuation of Study Drug	57
5.3.3 Lost to Follow-up	58
5.3.4 Replacements.....	58
6 Investigational Drug and Placebo	58

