2.2 Anticipated Benefit/Risk

Huntington's disease is a rare, progressive neurological disease¹. Currently available treatments for HD only mitigate symptoms and do not affect the underlying HD pathology, the disease course, or life expectancy after diagnosis of HD³². No approved treatments exist that can cure, slow, or reverse the course of HD. Based on the results of the nonclinical studies, WVE-003 has promise as a disease-modifying agent for the treatment of patients with HD. Target engagement was demonstrated both in vitro and in vivo. Nonclinical studies conducted in rats and monkeys yielded no toxicologically meaningful findings that would prevent initiation of clinical studies in HD patients.

[figure not shown]

2.3 Current Status of the Study and Dosing Paradigms as Recommended by the DEC and SMC

This is an adaptive study designed to evaluate data in an ongoing fashion to select and optimize dose levels and dosing frequencies. Data from Period 1 (SAD) have been reviewed by the DEC and SMC in accordance with [Section 4.4.1](#) and [Section 4.4.2](#), respectively, and recommendations were made regarding the number of cohorts, number of patients per cohort, and dose levels for Period 1 and P2C1.

In Period 1, the DEC/SMC have recommended dose escalation up to 90 mg. Initially, each cohort included 6 patients; however, due to variability in mHTT among patients, in , the DEC/SMC further recommended to expand each of the 3 single-dose cohorts to the cohort sizes listed below. Optional follow-up visits (up to 24 weeks postdose) were also added to provide the opportunity to obtain additional plasma and follow-up imaging samples prior to participation in Period 2. These additional data will be used to optimize the dose level:

- P1C1: 30 mg (n = 18; 2:1 active:placebo)
- P1C2: 60 mg (n = 18; 2:1 active:placebo)
- P1C3: 90 mg (n = 12; 2:1 active:placebo)

As of  the DEC/SMC recommended initiation of P2C1 with 30 mg administered Q8W through Week 16.

Subsequent dose levels, frequencies, number of cohorts, and number of patients per cohort will be determined based on DEC/SMC review of data from prior cohort(s) [REDACTED]

Section 4.4.1.3 [REDACTED]

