6.2.2 Administration of Investigational Drug

Study drug (WVE-003 or placebo) will be administered by IT injection by direct lumbar puncture using an atraumatic needle, and the total volume of the injection will be 20 mL. WVE-003 will be diluted with aCSF provided by the Sponsor and administered in a volume of 20 mL, as described in the Pharmacy Manual. The lumbar puncture will be performed by a physician who is experienced in lumbar puncture procedure and drug administration and appropriately trained for the study. Within 1 week prior to the lumbar puncture, a blood sample will be tested locally for platelet count and prothrombin time to confirm that it is safe to proceed with the lumbar puncture ([Section 8.2.8](#)). Patients should not be sedated during administration of study drug. Imaging is allowed to guide lumbar puncture if needed. Detailed instructions on the procedure to be used for lumbar puncture are provided in the Study Operations Manual.

Within approximately 15 minutes prior to administration of study drug, CSF samples will be collected for safety assessments ([Section 8.2.8](#)), concentration of WVE-003 ([Section 8.3](#)), and PD ([Section 8.4](#)), per the Schedule of Assessments. Additional CSF collected will be stored and used for research purposes. Approximately 20 mL of CSF total should be collected.

Immediately after each administration of study drug, all patients should be ambulatory and active for approximately 30 minutes postdose. The Investigator should note any weakness or fatigue during this period. In addition, formal physical examinations targeting the neurological system will be performed at the time points noted in the Schedule of Assessments. Any postdose SAEs will be monitored until resolution.

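### The PD model in Section 11.3.3 drops the baseline covariate without a stated reason, which in Period 1 usually costs some precision and leaves part of any baseline difference in the dose-versus-placebo contrasts

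*Combined protocol and SAP*

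**What the plan says.** For clinical endpoints, Section 11.3.2 states: "The MMRM will include the relevant baseline measure and factor variables for time, dose group and time by dose group interaction". The covariance is unstructured. For PD biomarkers (mHTT, wtHTT, NfL and others), Section 11.3.3 says the same model "will be applied with the exception that the baseline measure will not be included". No reason is given there, in the synopsis, in Section 11.3 or elsewhere in the supplied text.

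The synopsis makes change from baseline the response for both kinds of endpoint and adds: "The MMRM will be used to construct 95% confidence intervals and to test for differences between dose groups and placebo".

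Other provisions that bear on the point:

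- **Baseline sample (Section 6.2.2).** "Within approximately 15 minutes prior to administration of study drug, CSF samples will be collected for safety assessments"; the same sentence lists PD among the uses.
- **Period 1 sizes (Section 2.3).** Cohorts of 6 were expanded "due to variability in mHTT among patients" to 18, 18 and 12. The last reads "P1C3: 90 mg (n = 12; 2:1 active:placebo", and the other two have the same allocation.
- **Placebo (Section 11).** "Patients receiving placebo will be pooled to form a placebo control group for Period 1 and Period 2".
- **Period 2 baseline (Section 11.3).** It is "the measurement prior to the first dose of study drug in Period 2 for both new Period 2 patients and Period 1 rollover patients". A sensitivity analysis uses the value before the first Period 1 dose for rollover patients.
- **Rollover assignment (Section 7.3).** Rollover patients keep their Period 1 assignment.

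**The concern.** Subtracting baseline is not the same as adjusting for it. A change score forces the slope of follow-up on baseline to be 1. If the true slope is below 1, as it is with imperfect correlation and similar SDs, the change score over-corrects. The group with the higher baseline then appears to fall more, and the residual variance is larger than it need be. Section 11.3.2 itself models change from baseline with the covariate included, so the plan already treats the two as compatible.

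What is at stake is the width of the PD intervals and how far each contrast depends on the baseline values the groups happened to have. Between-patient variability in mHTT was the stated reason for enlarging the Period 1 cohorts, and the baseline CSF sample is already taken.

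The pooled placebo adds to this. Cohorts are enrolled and randomised in sequence, so part of the placebo group was not randomised alongside a given dose. A baseline difference between cohorts enters the contrast in the same way as a chance imbalance.

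**Working it through.** The plan states no power, SD or precision, so there is no figure to reproduce. Section 11.1 says the sample size does not rest on hypothesis testing.

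**Inputs from the documents.** Sizes of 18, 18 and 12 at 2:1 give 12, 12 and 8 active and 6 + 6 + 4 = 16 placebo, so N = 48 in k = 4 groups. Section 8.3 gives four post-dose CSF visits in Period 1 (Weeks 2, 4, 8 and 12). The note to Figure 1 gives 11 + 6 + 6 = 23 patients in the DEC/SMC review.

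**Assumptions.** Correlation rho between baseline and follow-up, and r = follow-up SD / baseline SD. Neither is in the documents.

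**Formulas at one visit, baseline SD = 1.** Slope beta = rho × r.

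- Variance without the covariate: 1 + r² - 2·rho·r.
- Variance with it: r²(1 - rho²) × [1 + 1/(N - k - 2)]. The bracket is the expected cost of estimating the slope.

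At N = 48 the bracket is 1 + 1/42 = 1.0238. For example, at r = 1 and rho = 0.5, without: 1.00; with: 0.75 × 1.0238 = 0.768; SE change = √0.768 - 1 = -12.4%.

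Change in SE from adding the covariate, N = 48:

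| r | rho 0.5 | rho 0.7 | rho 0.9 |
|---|---|---|---|
| 0.9 | -17.3% | -12.3% | -8.9% |
| 1.0 | -12.4% | -6.7% | -1.4% |
| 1.1 | -8.5% | -2.9% | +1.2% |
| 1.25 | -4.4% | +0.2% | -1.4% |

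The worst case is beta = 1: √1.0238 - 1 = 1.2%. At N = 23 the bracket is 1 + 1/17 = 1.0588. The r = 1 row becomes -10.9%, -5.1% and +0.3%, and the worst case is √1.0588 - 1 = 2.9%.

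A finite-sample simulation (20,000 trials per setting, equal SDs) gave 95% intervals 14%, 7% and 1% wider without the covariate at rho 0.5, 0.7 and 0.9. A four-visit MMRM check with equal correlations and 10% missing data (assumed) gave variance ratios of 1.32, 1.18 and 1.05.

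**Baseline difference left in the contrast.** The unadjusted contrast carries -(1 - beta) times the baseline difference. Treating all 48 as one randomisation, the SD of a chance difference is √(1/12 + 1/16) = 0.38 baseline SD for 30 or 60 mg, and √(1/8 + 1/16) = 0.43 for 90 mg. A one-SD imbalance moves the contrast by (1 - rho·r)/√(1 + r² - 2·rho·r) of its own SE: 0.50, 0.39 and 0.22 at r = 1, and 0.43, 0.28 and 0.02 at r = 1.1. Only 6, 6 and 4 of the 16 placebo patients belong to the same cohort as the 30, 60 and 90 mg patients, so baseline differences between cohorts would come on top of this.

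**False positives.** In a single-visit simulation over the same grid (8,000 trials per cell, one randomisation of 48), type I error was 0.045 to 0.054 without the covariate and 0.046 to 0.053 with it.

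**One common slope or one per visit.** The bounds above need a visit-specific slope, or slopes that are equal across visits. Large-sample results for one common slope with unstructured covariance:

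- rho falling 0.9, 0.8, 0.65, 0.5 over the visits, equal SDs: the last-visit gain is 8.7%, 6.9% or 3.1% at residual inter-visit correlation 0, 0.3 or 0.6, against 13.4% with visit-specific slopes.
- rho 0.9, r falling 1.1, 1.0, 0.9, 0.8: the first-visit SE rises by 5.3%, 6.7% or 10.3%, although the last visit gains.

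**Period 2.** If all planned sizes hold, 48 + 24 - 54 = 18 of the 24 P2C1 patients would be rollovers. Assume 6 new patients, 2:1 allocation, equal variances and correlations, a carry-over of -0.5 SD and an additional effect of -1.0 SD. For change from the Period 2 baseline, the unadjusted contrast averages -1.00. Adjusting for the value taken after the Period 1 dose gives -1.18, -1.11 and -1.04 at rho 0.5, 0.7 and 0.9, which mixes carry-over into the effect. Adjusting for the value before the first study dose gives -1.00, with an SE 1.4% to 2.3% larger. In the Section 11.3 sensitivity analysis, that covariate changes the SE by -10.9%, -5.6% and +0.6%.

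**The case against.** The exception is explicit, so it may be deliberate. Unadjusted change from baseline is a valid analysis. Section 11.3.6 says the SAP will be finalised before any interim analysis, and a reason could appear in SAP text that was not supplied. A single unadjusted model for both periods is also coherent, given that the Period 2 baseline of rollover patients is a poor covariate. PD is exploratory, and rho and the SDs are unknown. At rho 0.9 the gain is 1.4% or less for r from 1.0 to 1.25, and in one cell it is a small loss. All of this stands, and it limits the point to a minor one.

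It is also true that copying the single main effect from Section 11.3.2 would not secure the gain. When slopes differ across visits, a common slope can lose much of it or make one visit worse. This stands too, and is why the fix needs a baseline-by-visit term.

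A reader might infer that omitting baseline biases the contrasts or inflates false positives. The documents do not support that. With a pre-treatment baseline and randomised groups, the omission leaves expectation and type I error intact, and the carry-through is conditional on the imbalance that occurs. The partly non-concurrent placebo does weaken an appeal to randomisation, but that comes from pooling. The covariate removes only the part of a cohort difference that runs through baseline.

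A reader might also infer that these contrasts decide the dose. Section 2.1 says PD data were among those reviewed before P2C1 was recommended, but nothing says the MMRM contrasts were the basis.

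**Conclusion.** The point holds as a minor loss of precision in Period 1. Section 11.3.3 removes a covariate that Section 11.3.2 uses, without a stated reason and although the sample is already collected. At one visit, with equal SDs and 48 patients, the covariate is worth about 12%, 7% or 1% of the SE at rho 0.5, 0.7 or 0.9. The gain is larger if follow-up SDs are smaller than at baseline, and small or absent if they are larger.

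The worst expected loss of 1.2% at 48 patients, or 2.9% at 23, applies only with visit-specific or equal slopes. A reader might take it as a general guarantee for any baseline adjustment, but the common-slope results show that it is not. All sizes rest on assumed rho and SD ratios. What is certain from the text is the unexplained exception and the direction of the usual effect.

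**What to change.** In Section 11.3.3, and in the SAP, replace the exception for Period 1 with the last value before the first study dose, on the analysis scale, plus its interaction with visit. If the sponsor prefers to keep the unadjusted model, state why.

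For Period 2, say that a rollover patient's value taken after a Period 1 dose will not be used as a covariate. Use the value before the first study dose in the sensitivity analysis of Section 11.3, where change and covariate then share one baseline, or leave the Period 2 analysis unadjusted.

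The cost is a wording change and a few degrees of freedom for the visit-specific slopes. No new samples or visits are needed.

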11.3.4 Analysis of Safety Data

The summary of safety results will be presented by dose group. All safety analyses will be performed on the safety population using the following common rules:

- The baseline value is defined generally as the last available value before randomization.
- Adverse event observation periods are defined as follows:
 - Pretreatment AEs are AEs that developed or worsened prior to the first dose of study drug.

- On-treatment adverse events are AEs that developed or worsened from the first dose of study drug to study completion/discontinuation. Summaries of TEAEs will include all on-treatment AEs.
- For quantitative safety parameters based on central laboratory/reading measurement, descriptive statistics will be used to summarize results and change from baseline values by visit and treatment group.

11.3.4.1 Adverse Events

Treatment-emergent AEs, TEAEs assessed as related to study drug or to study procedures, treatment-emergent SAEs will be summarized for each dose group based on MedDRA coding of verbatim terms reported by investigators.

Adverse event incidence tables will present, by SOC and PT, the number and percentage of patients experiencing an AE, the number and percentage of patients experiencing an AE by severity and by relationship to treatment.

Listings of all AEs, SAEs, deaths, and AEs leading to study discontinuation will be provided.

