2 RATIONALE FOR THE STUDY

This initial clinical study with WVE-003 was designed to evaluate the safety and tolerability of single ascending dose (SAD) cohorts followed by multiple ascending dose (MAD) cohorts. Information on the safety, tolerability, PK, pharmacodynamics (PD), and clinical effects of WVE-003 will inform dose selection for subsequent clinical studies.

As the primary endpoint is the safety and tolerability of WVE-003, placebo is the most appropriate comparator for this study. It is also important to distinguish between drug-related and procedure-related adverse events, which is difficult in a limited number of patients. Therefore, performing lumbar punctures in patients receiving placebo will be crucially important for comparison. Furthermore, one vital objective is to evaluate the biologic response to the study drug, which will be measured using mHTT levels in CSF. It is important to understand the natural variability in the level of mHTT in CSF within a single patient as well as between patients in order to accurately interpret these mHTT measurements. In addition to trying to establish whether or not mHTT lowering occurred, demonstration of dose response would be important in the planning of subsequent studies. Together with exposure data, mHTT lowering at different doses will form the basis of modeling to identify the optimal dose(s) and dosing interval in subsequent studies.

The volume of injection with artificial CSF (aCSF) is 20 mL, and an equivalent volume of CSF will be withdrawn for bioanalysis and to maintain CSF pressure. It is a relatively small volume compared to the total volume of CSF in humans, which is approximately 150 mL (range – 130 to 160 mL), with normal production rate of CSF being approximately 500 mL per day²⁸.

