4.4.3.3 Individual Stopping Criteria

Dosing will be stopped for an individual patient at any time in the study if:

- A patient experiences a serious or intolerable adverse event (AE) that, in the Investigator's opinion, requires study drug discontinuation.
- A patient experiences a TEAE that is severe in intensity and related to administration of WVE-003 (except TEAEs associated with lumbar puncture).

The patient will be followed up for safety per protocol. Per the Investigator's judgement, the patient may be allowed to resume participation in the study if or when the event has resolved]. Dosing may be resumed for individual patients upon recovery from the severe event and if supported by the Investigator, based on their assessment of the benefit/risk balance for the patient.

4.4.3.4 *Adverse Events That are Exempt from Stopping Criteria*

Intrathecal administration of drugs is known to result in untoward effects such as post-lumbar puncture headache, pain, etc.^{33,34} Given the common occurrence of such side effects following lumbar puncture, it is anticipated that patients may experience AEs temporal to the IT administration procedure that are not attributable to study drug^{33,34}. Therefore, the AE terms listed in [Table 5](#) will be exempted from the assessment of Stopping Criteria:

Table 5 Adverse Event Preferred Terms Exempted From Stopping Criteria

Preferred Terms Exempt From Stopping Criteria	
Administration site bruise	Instillation site bruise
Catheter site bruise	Post-lumbar puncture syndrome
Infusion site bruising	Post-procedural discomfort
Infusion site discomfort	Post-procedural contusion
Infusion site pain	Procedural headache
Injection site bruising	Procedural pain
Injection site discomfort	Traumatic lumbar puncture
Injection site pain	

Abbreviations: AE = adverse event; MedDRA = Medical Dictionary for Regulatory Activities; PT = Preferred Term.

Note: AEs exempted from the Stopping Criteria include the MedDRA PTs listed above and their associated verbatim terms.

While these procedural events are exempt from Stopping Criteria review, they will be recorded as AEs as described in [Section 9](#). In addition, as part of their ongoing review of unblinded safety data, the SMC will carefully review the above-referenced exempted AE terms to ensure there are no meaningful imbalances between treatment groups.

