Period 1 Urine PK: Samples will be collected on Week 0/Day 1 from 0-4 hours, 4-8 hours, and 8-24 hours postdose.

Period 1 CSF PK: Samples will be collected predose on Week 0/Day 1, as well as Week 2, Week 4, Week 8, and Week 12. A sample will also be collected at the ET visit, if the patient discontinues early.

Period 2 Plasma PK: At the first and last dosing visit, blood samples will be collected predose (within 4 hours prior to dosing), and postdose at 30 minutes (± 5 minutes), 1 hour (± 15 minutes), 2 hours (± 15 minutes), 4 hours (± 30 minutes), and 6 hours (± 30 minutes). New patients only will also have a sample collected on Day 1 at 24 hours (± 2 hours) postdose. For any other dosing visit, blood samples will be collected at 2 hours (± 1 hour) postdose. In addition, plasma PK samples will be collected once at all non-dosing clinic visits. A sample will also be collected at the ET visit, if the patient discontinues early.

Period 2 CSF PK: Samples will be collected at all clinic visits (Week 0/Day 1, Week 4, Week 8, Week 12, Week 16, Week 20, Week 24, and Week 28). The sample will be collected predose on dosing visits. A sample will also be collected at the ET visit, if the patient discontinues early.

The date and time of the sample collection will be recorded.

Samples will be analyzed by a central laboratory to determine concentrations of WVE-003 using validated methods (plasma and CSF) or qualified methods (urine).

Samples will only be used by the Sponsor and/or a contracted vendor for research related to the development of treatments for HD and stored for a maximum of 10 years. All biological material will be stored and secured in a way that ensures that unauthorized access is prohibited and the samples are not lost, deteriorated, or destroyed accidentally or illegally. Detailed instructions for sample collection, storage, processing, and shipping will be provided in the Laboratory Manual.

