9.1 Eliciting and Documenting Adverse Events

All AEs reported or observed during the study, including AEs resulting from concurrent illnesses, reactions to concurrent medications, or progression of disease states, will be recorded on the AE page in the eCRF and in the site source notes. The eCRFs used to document AEs are designed to help ensure this information is collected in a standard way. Information to be collected includes event term, date and time of onset, date and time of resolution, Investigator-specified assessment of severity and relationship to study drug, action taken with respect to study drug, seriousness, any required treatment or evaluations, and outcome. All AEs will be followed until the ET or EOS visit, at a minimum. The sites will be provided with completion guidelines for the eCRF, which will further guide them on how to record the data, including AEs. The MedDRA will be used to code all AEs.

Any medical condition that is present at the time that the patient signs informed consent but does not worsen should not be reported as an AE. However, if it worsens at any time during the study, it should be recorded as an AE. This includes any spontaneously reported worsening of depression, i.e., not based on the study rating scales.

In addition to observations of the patient, AEs identified from any study data (e.g., laboratory values, physical examination findings, ECG changes) or identified from review of other documents that are considered clinically significant will be documented on the AE page in the eCRF. Worsening of symptoms that are only detected on clinical effects rating scales will not be reported as AEs.

Adverse events will be assessed at each visit by direct questioning as well as elicited from physical examination by site staff. In addition, all sites in the study must ensure patients have a 24-hour telephone number to contact medical site staff for the duration of the study, in case of emergent AEs or SAEs.

If there is any doubt as to whether a clinical observation is an AE, the event should be reported.

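### For terms that lumbar punctures also cause, one undivided adverse event window over 5 or 8 punctures dilutes a dosing-related difference; a table by puncture interval would recover it

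*Combined protocol and SAP*

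**What the plan says.** - **Aim.** Section 2 gives the reason for puncturing placebo patients: "It is also important to distinguish between drug-related and procedure-related adverse events, which is difficult in a limited number of patients". Safety and tolerability is the primary objective (Section 3).
- **Statistic.** Section 11.3.4.1: "Adverse event incidence tables will present, by SOC and PT, the number and percentage of patients experiencing an AE". These are patient counts. They are also broken down by severity and by relationship; "TEAEs assessed as related to study drug or to study procedures" are summarised, and all events are listed.
- **Window.** Section 11.3.4: "On-treatment adverse events are AEs that developed or worsened from the first dose of study drug to study completion/discontinuation". It is not divided by dose, by puncture or by time since injection.
- **Punctures.** Section 8.3 on CSF sampling. Period 1: "Samples will be collected predose on Week 0/Day 1, as well as Week 2, Week 4, Week 8, and Week 12". Period 2: "Week 0/Day 1, Week 4, Week 8, Week 12, Week 16, Week 20, Week 24, and Week 28". Period 1 gives one dose (4.1.3.1). The first Period 2 cohort is dosed at Weeks 0, 8 and 16 (4.1.4.3).
- **Puncture terms.** Section 4.4.3.4 treats side effects after puncture as common and exempts the Table 5 terms from the stopping criteria. The SMC reviews those terms unblinded "to ensure there are no meaningful imbalances between treatment groups".
- **Data.** Section 9.1 collects "date and time of onset, date and time of resolution" for each event.

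**The concern.** Each patient counts once per term over the whole window. Four of the five Period 1 punctures, and five of the eight in Period 2, deliver no study drug but can produce the same headache or pain terms in both arms. A patient who would have had a procedural headache after a later sampling puncture is already a case, whether or not the injection also caused one. A difference that arises only after injections therefore shrinks towards zero in the ever/never percentage.

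Both arms follow the same puncture schedule, so this is lost sensitivity and not confounding. What is at stake is how well the placebo punctures do the job that Section 2 gives them, for the group of terms in which drug and procedure are hardest to tell apart.

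**Working it through.** The plan states no event rate, effect size or power for this comparison, so there is no figure to reproduce.

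**Inputs from the documents**
- Punctures L and dosing punctures D: 5 and 1 in Period 1; 8 and 3 in Period 2.
- The Week 28 puncture falls on the end-of-study visit, where routine event collection stops (Table 3, Section 9). About 7 punctures in Period 2 therefore have follow-up.
- Period 1 size (2.3): 18 + 18 + 12 = 48 at 2:1, giving 12, 12 and 8 active by dose (32 pooled) and 16 pooled placebo.

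**Assumptions**
- Background risk p per puncture for one term.
- The drug adds d at dosing punctures only.
- Punctures are independent.

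**Formula**
- Placebo, ever: 1 - (1-p)^L
- Active, ever: 1 - (1-p)^(L-D) × (1-p-d)^D
- Difference: (1-p)^(L-D) × [(1-p)^D - (1-p-d)^D]

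The bracket is the risk difference over the dosing intervals. The share of it that survives in the ever/never table is (1-p)^(L-D), whatever the value of d.

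| p | Period 1, (1-p)^4 | Period 2, 8 punctures, (1-p)^5 | Period 2, 7 punctures, (1-p)^4 |
|---|---|---|---|
| 0% | 100% | 100% | 100% |
| 2% | 92% | 90% | 92% |
| 5% | 81% | 77% | 81% |
| 10% | 66% | 59% | 66% |
| 20% | 41% | 33% | 41% |
| 30% | 24% | 17% | 24% |

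More than half is lost only above p = 1 - 0.5^(1/4) = 16% in Period 1, or 1 - 0.5^(1/5) = 13% with all 8 Period 2 punctures. A patient who rolls over straight after Week 12 has little Period 1 follow-up of that puncture. With exponent 3, the Period 1 shares at 5%, 10% and 20% become 86%, 73% and 51%.

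**Example, p = 20%, d = 30 points, Period 1.** Dosing interval: 50% v 20%, difference 30 points. Ever/never: 1 - 0.8^4 × 0.5 = 79.5% v 1 - 0.8^5 = 67.2%, difference 12.3 points (30 × 0.41).

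**Detectability.** No test of adverse events is planned. Exact two-sided Fisher power at 5% serves only as a yardstick (Period 1, 16 placebo):

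| Plain v drug puncture | Pooled 32 active: ever / interval | 12 active: ever / interval | 8 active: ever / interval |
|---|---|---|---|
| 1% v 20% | 25% / 26% | 15% / 18% | 16% / 18% |
| 2% v 15% | 10% / 7% | 7% / 7% | 8% / 8% |
| 5% v 20% | 9% / 15% | 8% / 10% | 6% / 11% |
| 5% v 35% | 29% / 64% | 23% / 40% | 16% / 38% |
| 10% v 40% | 19% / 53% | 10% / 37% | 10% / 32% |
| 20% v 50% | 12% / 44% | 6% / 34% | 3% / 24% |

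The planned tables are by dose group, so the last two columns are closer to what a reader of them will see.

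**If the effect is not confined to dosing.** Let the drug add 10 points in all five Period 1 intervals, with p = 5%. Ever/never is then 1 - 0.85^5 = 55.6% v 1 - 0.95^5 = 22.6%, power 52% (32 v 16). The first interval alone gives 15% v 5%, power about 4%. The ranking reverses.

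**The case against.** **The model assumes that the drug acts only after injections.** This is the strongest objection, and it stands. Section 5.2.1.2 equates 5 months with 5 elimination half-lives, about a month each, and 4.1.3.2 requires Week 12 to be completed for washout. Patients on active drug are therefore still exposed at the sampling punctures. For late or persistent effects the full-window table is better, so the interval table can only be an addition.

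**The rates are assumed.** This also stands. At 5% or below, 77% or more of the difference survives. A term that punctures do not cause loses nothing, and small excesses are hard to see on either scale.

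**Other summaries exist.** Relationship to drug and to procedure is recorded and tabulated, and repeat events remain in the listings with their onset. This helps in part: attribution can separate events after sampling-only visits. On dosing days, however, CSF is drawn about 15 minutes before the injection at the same visit (6.2.2), and attribution is blinded judgement. A listing is not a comparison between arms.

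**The SMC charter and the SAP may already provide such tables.** Section 11.3.6 refers to both, and neither is in the text reviewed. This is possible, so the request is to confirm or add.

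A reader might go further and infer that puncture events swamp any drug effect, that both arms approach a ceiling, that ever/never incidence is the only event summary, or that the SMC check is the sole safeguard for the exempted terms. The documents support none of these. The first two need high per-puncture rates that are not given; the third overlooks the severity and relationship tables and the listings; and the exempted terms are still recorded and reported as adverse events.

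**Conclusion.** The point holds for a defined group of terms. Where punctures themselves cause the event and the drug effect falls in the interval after dosing, the planned patient-level table shows (1-p)^4 of the Period 1 difference: about 81%, 66% and 41% at background risks of 5%, 10% and 20% per puncture. In Period 2 the factor is the same with 7 punctures followed up, or (1-p)^5 with 8. These figures rest on an assumed p, independent punctures and no drug effect after sampling punctures.

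The planned tables are not wrong and are not biased by unequal exposure. They leave out one randomised comparison, at the moment when drug and puncture coincide, although the data for it are already collected. Importance: between a suggestion and a recommendation.

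**What to change.** In 11.3.4.1, keep every planned table and add one set by puncture interval:

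1. **Period 1.** Incidence of treatment-emergent events with onset from the Day 1 injection up to the Week 2 puncture, by dose group and pooled active against placebo, shown beside incidence after the sampling-only punctures.
2. **Period 2.** Number and percentage of injections followed by the event before the next puncture, and the same for sampling-only punctures, by dose group and pooled active against placebo. Give 95% confidence intervals for the active-placebo difference that treat the patient as the cluster.
3. **SMC.** Make the same tabulation of the Table 5 terms available for the imbalance review, unless the charter already provides it.

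State that the set is descriptive and that the full-window tables remain the reference for late or persistent effects.

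**Cost.** Some SAP wording and a few tables, with no new data collection. Late-onset events can cross the interval cut-off. Period 1 intervals also differ in length (2, 2, 4 and 4 weeks up to Week 12), so arms should be compared within the same interval.
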